# Aims for Phase II:

AIM 1. Compare F4C to a standard BIP in its efficacy to reduce FV by decreasing fathers' violent behavior, improve father-child interactions, and reduce child mental health symptoms. *Hypotheses.* Children of fathers who receive F4C (n=140), relative to BIP (n=140), will: (1a) experience less FV, (1b) have more positive father-child interactions, and (1c) have lower FV-related mental health symptoms (PTSD, internalizing/externalizing) at post treatment and 6- and 12-month follow-ups. The effects of both treatments on father and coparent mental health outcomes will also be examined (1d *exploratory*).

AIM 2. Identify and compare latent change profiles of therapeutic targets (RF, ER) in F4C and BIP fathers across the 18-week intervention. *Hypotheses*. Compared to BIP, more F4C fathers will show profiles of healthy change in therapeutic targets: (2a) masked coding of insession RF/ ER (i.e., increased RF and adaptive ER, decreased maladaptive ER), and (2b)

between-session self-reported RF/ ER (i.e., increased RF and adaptive ER, decreased maladaptive ER). F4C change profiles will reveal critical junctures in treatment that precipitate change, thereby serving to optimize timing/delivery of treatment components (2c, *exploratory*).

AIM 3. Examine the mediating role of therapeutic change targets (RF, ER) on child-related outcomes in F4C and BIP families. *Hypotheses*. Profiles of healthy change in RF and ER will mediate the treatment effect of F4C over BIP on: (3a) FV (3b) father-child interactions, and (3c) child mental health symptoms (PTSD, internalizing/externalizing) at post-treatment and at 6- and 12-month follow-ups.

2. **Background:** Describe the background information that led to the plan for this project. **Provide references** to support the expectation of obtaining useful scientific data.

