Eighteen percent of children in the United States witness Intimate Partner Violence (IPV) in their homes with significant immediate and long-term consequences to physical and psychological health. Exposure to IPV perpetrated by fathers is common among children referred to child protective services with both national and state level data indicating between 30-40% of child welfare reported children are exposed to IPV, which is most often perpetrated by a father figure. Child protective service systems have long focused on mothers in their interventions for both safety and treatment of IPV. Mothers have been tasked with protecting their children from witnessing IPV or risk losing their children.  Further, all the treatment requirements and opportunities are provided to and expected to be carried out by mothers. Fathers are not held accountable nor are they expected to participate in treatments often due to a belief that interventions do not work for this population. This belief comes from several metaanalyses that report near zero effect sizes of current batterer group intervention programs (BIPs). the only broadly available treatment for IPV perpetrators, in reducing violence. Beyond negligible effects, attrition rates, even for court-mandated programs, are high (30-60%) indicating a significant service need. Importantly, even among intervention completers, recidivism rates for BIPs can be 20-30% indicating high intervention failure.  Often, men who continue to use violence following completion of a group BIP are re-referred to the same program or another similar group program of greater length. Others may serve a short jail sentence with no other treatment provided. Families with IPV are frequently involved with child protective services because it is well known that exposure to IPV is detrimental to children and increases their risk for psychosocial and psychiatric difficulties. (12-14) Despite their ineffectiveness child protective services and the courts in many states continue to use completion of BIPs as sufficient to grant child visitation or as evidence that child protective oversight is no longer needed (15, 16)

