# Preliminary Studies F4C development.

First, F4C was developed and piloted by the PI in an outpatient clinic setting. A sample of 10 fathers were referred by child protection and the courts to participate in an open trial of initial feasibility. Completion rates were 80% and all fathers who completed the program remained non-violent during treatment with very high satisfaction indicating good potential for intervention acceptability. Next, using content, treatment manuals, and training materials developed during the pilot study outlined above, [name] trained 12 clinicians in

community mental health clinics to deliver F4C to child protection involved families through a statewide initiative in CT. Based on session fidelity reviews it is clear clinicians have successfully implemented the intervention using the manual and training curriculum. Based on a sample of 73 fathers referred to F4C, 74% completed the program. Importantly 68% of those referred to F4C had previously participated in a BIP. Additionally, fathers self-reported significant improvements

in the intervention targets of emotion regulation and reflective functioning from pre to post intervention (p<.05). There were significant reductions in IPV post-intervention based on mothers and fathers reports (see Figure 2) and significant reductions in child maltreatment risk based on the Parental Acceptance Rejection Questionnaire (t (67) = 6.44, p < .00) These data support F4C's ability to improve hypothesized intervention targets and IPV and child maltreatment outcomes. The current study is needed to provide an initial randomized test of F4C compared to an individually delivered BIP and group BIP. The randomized three group study will allow us to test F4C compared to BIP-I and Group BIP (BIP-G) and indicate whether the individual treatment format is the driving factor OR the content OR both.

3. **Research Plan:** Summarize the study design and research procedures using non-technical language that can be readily understood by someone outside the discipline. If working with a Non-Government Organization (NGO) or other organization, be sure to highlight which are research-only activities and which activities would occur regardless of the research. If working with survey firms, please specify what research activities the research firm will be responsible for.

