# Phase II Hypotheses:

**AIM 1 Hypotheses:** Children of fathers who receive F4C (n=180), relative to BIP (n=180), will: (1a) experience less family violence (FV), (1b) have more positive father-child interactions, and (1c) have lower FV-related mental health symptoms (PTSD, internalizing/externalizing) at post treatment and 6- and 12-month follow-ups. The effects of both treatments on father and coparent mental health outcomes will also be examined (1d exploratory). Hypotheses will be evaluated with the broad family of latent (growth) curve models (LGM), which estimate and compare trajectories of change for each case in the data. Group differences in changes will be tested in multiple group LGM models. Following analyses for our primary study hypotheses, we will examine whether child sex moderates child mental health outcomes between the F4C and BIP groups. Power. The planned sample size of 140 F4C and 140 BIP cases provides power of .91 to detect a small to moderate effect size (d = 0.12). The current study with 140 per group (even 126) per group assuming a conservative 30% attrition at follow-up) has sufficient power to determine small differences in changes between intervention groups on outcomes. LGM models for changes in latent rather than observed scores, for three or more waves of data, have the advantage of partialing out measurement error, and increasing the statistical power by at least 20%. See Statistical Design and Power Section for estimation method.

AIM 2 Hypotheses. Compared to BIP, more F4C fathers will show profiles of healthy change in therapeutic targets: (2a) masked coding of in-session RF/ ER (i.e., increased RF and adaptive ER, decreased maladaptive ER), and (2b) between-session self-reported RF/ ER (i.e., increased

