NOTE: Is this research proposal designed to enroll children who are wards of the state as potential participants?  $\square$  Yes  $\square$  No

It is possible that the children of some enrolled fathers will be placed in foster care and under the guardianship of the Department of children and families at the time of referral. These children would only be enrolled if there was planned reunification with the father.

7. **Inclusion/Exclusion Criteria:** What are the criteria used to determine participant inclusion or exclusion?

**Inclusion Criteria**. Men who (1) report an incident of IPV (pushing, slapping, kicking) within the last 12 months prior to screening (based on court/police records, partner or self- report); (2) have at least one biological child aged 9 months to 12 years with whom they have contact in person or by phone/facetime etc. at least monthly; (3) are able to complete assessments in English; and (4) agree to have their female coparents (mother of the youngest child) contacted as collateral informants and for consent for participation of their shared child. If a participant has more than one child in the age range, the youngest will be the target of assessment. Female coparents (the

target child's biological mother who does not need to be in a relationship with the father at the time of the study) will be contacted to consent for participation of herself and their shared child. If the coparent declines participation of the child the father may still participate in the study if he meets eligibility criteria to prevent any possible retaliation against co-parents for not consenting to child participation. No information about contact with co-parents or their responses will be provided to the fathers

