# 4. How was this estimate derived?

Phase I: Seventy-five fathers, the female co-parent of their youngest child, and their child will participate for a total of up to 225 participants. We intend to include all 75 fathers assigned to study interventions for intent to treat analysis. The planned sample size of 75 participants who will provide data for inclusion in our intention-to-treat analysis should provide sufficient power to detect clinically meaningful differences between and within treatment conditions as specified in our primary aims. A sample of 63 people provides power of 80% to detect a standardized treatment group differences at 18 weeks of d = 0.45. For purposes of power estimates, we assumed d = 0.45 will represent a potentially meaningful clinical difference in both our primary and mechanism outcomes. In a pilot study examining F4C on participant IPV effect size for outcome was d = 0.86. We will enroll 75 participants to accommodate a 16% loss to follow-up.

Using these procedures in prior studies, our rate of successful follow-up has ranged from 70-90%. With 280 participant families randomized and an aim of at least 70% completion, we expect to have 196 cases with complete treatment and follow-up data.

**4. Process of Consent/Assent** (*NOTE: When a study includes minors, parent provide permission [not consent] for the child's participation, and the child provides assent for participation)* 

Describe the setting and conditions under which consent/assent will be obtained, including parental permission or surrogate permission and the steps taken to ensure participants' independent decision-making.

Fathers will complete informed consent either in person or online via Yale's REDcap data system, in line with guidance on obtaining informed consent during the COVID-19 pandemic. Each will agree to have their female co-parent contacted for consent of participation of their shared child.

Mothers will complete informed consent related to their own participation and the participation of children in which they are the primary guardian. This will be completed online via Yale's REDcap system..

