Children will be recruited into this study to participate in brief self-reports of their symptoms (for those 7 and older) and father-child observational assessments. This will provide an observational measure of father-child interactions providing an additional measure of change related to parenting and child maltreatment risk. Fathers will be able to participate without their children to reduce any risks to the children for retaliation for their lack of participation. Study research assistants will describe the study procedures to the child and ask if they would like to participate. Verbal agreement to participate and behavioral compliance without undue pressure from the father will be taken as assent from children under 7. For those over 7 a written assent will be collected. If a play session cannot begin or must be ended, father and child will be compensated for the attempt to provide data to minimize risk to the child for being uncooperative. If a play session

or child report assessment does not proceed, the father will continue in the study to randomization and treatment assignment.

6. Documentation of Consent/Assent: Specify the documents or verbal scripts that will be used during the consent/assent process. Copies of all documents should be appended to the protocol, in the same format that they will be given or spoken to participants.

A script to introduce the play assessment to children is included with the protocol. RAs will use this script with children prior to beginning the sessions.

7. Non-English Speaking Participants: Explain provisions in place to ensure comprehension for research involving non-English speaking participants. Translated copies of all consent materials must be submitted for approval prior to use. Do you speak the local language? Will you require a translator? (If so, please elaborate on how the translators will be trained).

N/A this study will include English speaking only participants.

**8.** Are any of the study procedures likely to yield information subject to mandatory reporting requirements? (e.g. HIV testing – reporting of communicable diseases; parent interview -incidents of child abuse, elderly abuse, etc.). Please verify to whom such instances will need to be reported.

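### Hypothesis 1b is powered on 140 per arm, but 140 is only a ceiling because fathers can be randomised without their child; the stated 126 per group after 30% loss should be 98

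*Combined protocol and SAP*

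**What the plan says.** Section IV.1 (Aims for Phase II) states hypotheses 1a to 1c together: "Children of fathers who receive F4C (n=140), relative to BIP (n=140), will: (1a) experience less FV", followed by father-child interaction (1b) and child symptoms (1c). The Aim 1 text under Phase II Hypotheses in the Analytic Plan gives them a single power statement: "140 F4C and 140 BIP cases provides power of .91 to detect a small to moderate effect size (d = 0.12"). It then reduces the sample to 126 per group, "assuming a conservative 30% attrition at follow-up". The same paragraph opens with 180 per arm.

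The 1b outcome is coded from a video-recorded play session of the father with the target child (Table 1; Parent-Child Interaction Tasks).

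The entry rules do not require that session:
- Section IV.7, Inclusion Criteria: "If the coparent declines participation of the child the father may still participate in the study". The Initial screen text in Section IV.3 says the same.
- Section V.5: "Fathers will be able to participate without their children". If the play session or the child's self-report does not go ahead, the father is still randomised.
- Section VII.2, Protection of Child Participants, repeats the rule for the play session.

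Section V (How was this estimate derived?) reports past follow-up of 70-90% and concludes, for 280 families: "an aim of at least 70% completion, we expect to have 196 cases with complete treatment and follow-up data".

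**The concern.** A family with no play session at any wave contributes nothing to 1b, whatever model is fitted. The rules that allow this protect coparents and children and are not in question. They do have a sample-size cost, and no section counts it. A reader of the Aim 1 power text would take 1b to be as well powered as the hypotheses that do not need the child present.

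Two further figures blur the picture. The 126 per group does not follow from 140 and 30%, so the one allowance that is made looks smaller than it is. And the 196 is attached to complete treatment as well as follow-up data, although it rests on a single 70% that is called completion and is not defined. An intention-to-treat analysis needs the number of families with outcome data. Treatment completers are a different count.

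**Working it through.** **The plan's own figures.**
- 280 × 0.70 = 196, or 98 per arm. This reproduces Section V exactly.
- 140 × 0.70 = 98, not 126. The figure 126 equals 180 × 0.70, and the Aim 2 power text likewise carries 360 × 0.70 = 252. Both match 180 per arm, not the 140 now planned. From 140, a figure of 126 would mean a loss of 10%.
- Power of .91 at d = 0.12 does not reproduce as a two-group comparison of means: with 140 per arm it is 0.17 (two-sided 0.05). The growth-model inputs are not in the available text, so I cannot rework that figure and use a simple benchmark instead.

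**Dyads available for 1b.** No expected rate of child participation is given. I assume 70-90% and apply the plan's 30% loss independently:
- dyads per arm at baseline = 140 × c
- dyads per arm after loss = 140 × c × 0.70

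**Detectable difference.** For 80% power, two-sided 0.05, in SD units: d = 2.80 × √(2/n), n per arm.

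| Child participation c | Baseline per arm | After 30% loss | Detectable d after loss |
|---|---|---|---|
| 100% | 140 | 98 | 0.40 |
| 90% | 126 | 88 | 0.42 |
| 80% | 112 | 78 | 0.45 |
| 70% | 98 | 69 | 0.48 |

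The 126 in the 90% row is 140 × 0.90 at baseline. Its agreement with the plan's 126 is a coincidence.

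With 140 per arm and no loss, d would be 0.335. The move from 0.335 to 0.40 is attrition, which the plan already means to allow for. The child rule adds the rest: 0.02 to 0.08 SD.

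In terms of power, take an effect that has .91 power at 140 per arm in this comparison (d = 0.395). Power is 0.79 after attrition alone, and 0.745 to 0.64 with 90% to 70% child participation as well.

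**Can 196 also be treatment completers?** Inputs: for F4C, "Based on a sample of 73 fathers referred to F4C, 74% completed the program", and 80% in the open pilot of 10 fathers (Preliminary Studies). For BIP, the Background says "attrition rates, even for court-mandated programs, are high (30-60" per cent), so 40-70% complete.
- Completers with F4C at 74%: 140 × 0.74 + 140 × (0.40 to 0.70) = 103.6 + (56 to 98) = 160 to 202.
- Completers with F4C at 80%: 112 + (56 to 98) = 168 to 210.
- Completers also followed up, if follow-up of 70-90% is independent of completion: from 159.6 × 0.70 = 112 to 210 × 0.90 = 189.

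So 196 lies within the range of possible completers, but above the joint count under independence.

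**The case against.** The strongest reply is that 140 is the number randomised per arm, not a promised analysis set. The Phase II description words the total of 840 participants as a maximum, and Section V calls its 280 children a target. Child absence is permitted but not quantified, and nothing stops a child who missed the baseline session from attending a later one. Growth models can use families with partial data. All of this stands, and it is why 140 is called a ceiling here. A reader might infer that 1b must start below 140; the documents do not show that. But the power statement still allows for follow-up loss only.

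A reader might also infer that the 196 is wrong because it uses a follow-up rate alone. The text does not say so: it calls the 70% an aim of completion, and the phrase about treatment and follow-up data can mean data collected in both periods. Fathers who miss appointments are contacted for their data, and dropouts are pursued for intention-to-treat analysis. The completion rates are themselves indirect: the BIP range is background for existing programmes, not the individual format used here, and the 74% is of fathers referred, not randomised. They make a joint count of 196 optimistic but do not exclude it.

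Nor does a power figure fail for hypothesis 3b, since Aim 3 gives none. Hypothesis 1c is not caught in the same way: exclusion 7 requires the coparent's report of child symptoms. Section VII.2 lets a father stay if his partner declines for herself, and those two passages need reconciling.

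**Conclusion.** The point holds for 1b and for the 126. The power claimed for 1b is not supported, because it takes a ceiling as the sample and makes no allowance for absent children. The cost is moderate: a detectable difference of about 0.42-0.48 SD against 0.40 SD with attrition alone. That rests on assumed 70-90% participation, 30% loss independent of it, and a two-group comparison at two-sided 0.05. The planned latent growth models may do better or worse than this benchmark.

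The replacement of 126 by 98 rests on no assumption beyond the plan's own 140 and 30%. The 196 is correct arithmetic with an undefined meaning. That calls for a definition; the number is not shown to be wrong.

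**What to change.** In the Aim 1 power text and in Section V:
- State the families randomised (280) and the families expected with follow-up outcome data whatever their treatment completion (196, or 98 per arm, at 70%). Replace 126 by 98.
- State separately the dyads expected with play data for 1b, at baseline and after loss, under an explicit participation assumption. At 70-90% these are 98-126 and about 69-88 per arm.
- Restate the detectable difference for 1b on that number.
- In Section V, say whether the 70% means follow-up, treatment completion or both. Do not describe the 196 as treatment completers unless a stated completion rate supports it; expected completers by arm can be given as their own figure.

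The cost is a few restated sentences and a less favourable figure for 1b. Enrolment, procedures and the rules that let a father take part without his child stay as they are.

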# Preliminary Studies F4C development.

First, F4C was developed and piloted by the PI in an outpatient clinic setting. A sample of 10 fathers were referred by child protection and the courts to participate in an open trial of initial feasibility. Completion rates were 80% and all fathers who completed the program remained non-violent during treatment with very high satisfaction indicating good potential for intervention acceptability. Next, using content, treatment manuals, and training materials developed during the pilot study outlined above, [name] trained 12 clinicians in

community mental health clinics to deliver F4C to child protection involved families through a statewide initiative in CT. Based on session fidelity reviews it is clear clinicians have successfully implemented the intervention using the manual and training curriculum. Based on a sample of 73 fathers referred to F4C, 74% completed the program. Importantly 68% of those referred to F4C had previously participated in a BIP. Additionally, fathers self-reported significant improvements

in the intervention targets of emotion regulation and reflective functioning from pre to post intervention (p<.05). There were significant reductions in IPV post-intervention based on mothers and fathers reports (see Figure 2) and significant reductions in child maltreatment risk based on the Parental Acceptance Rejection Questionnaire (t (67) = 6.44, p < .00) These data support F4C's ability to improve hypothesized intervention targets and IPV and child maltreatment outcomes. The current study is needed to provide an initial randomized test of F4C compared to an individually delivered BIP and group BIP. The randomized three group study will allow us to test F4C compared to BIP-I and Group BIP (BIP-G) and indicate whether the individual treatment format is the driving factor OR the content OR both.

3. **Research Plan:** Summarize the study design and research procedures using non-technical language that can be readily understood by someone outside the discipline. If working with a Non-Government Organization (NGO) or other organization, be sure to highlight which are research-only activities and which activities would occur regardless of the research. If working with survey firms, please specify what research activities the research firm will be responsible for.

Phase I: Seventy five fathers of children aged 6 months to 11 years will be referred by the Department of Children and Families to the Parent and Family Development Program at Yale, recruited and randomized to either F4C BIP-I or BIP-G (n = 25 per group) following an initial screen and baseline assessment.

